**9.3.3 Covariate Assessment**

The patient and clinical characteristics listed below will be collected from medical records to provide descriptive information on the Blincyto-treated study population and as consideration for use as stratifying variables or for standardization:

- Patient age at date of treatment initiation (in years)
- Patient sex (male/female)
- Blincyto indication (eg, R/R ALL, MRD+ ALL, etc)
- ALL disease characteristics and treatment since disease diagnosis, during Blincyto treatment and through to end of study:
  - Date of ALL diagnosis
  - R/R status (yes/no for each)
  - MRD status in morphological CR
  - First relapse within 12 months of front-line treatment (yes/no)
  - Cytogenetics
  - Bone marrow blasts (%) at Blincyto initiation
  - Number of prior relapses
  - Prior ALL treatment regimens (number and type of treatment, including allogeneic HSCT and dates, and response to prior treatment regimens)
  - ALL treatment regimens after Blincyto completion

- Disease characteristics for indication other than ALL treatment since disease diagnosis, during Blincyto treatment (indication, date of diagnosis, prior treatment)
- Concomitant medications 7 days prior to Blincyto initiation, during Blincyto treatment and up to 30 days after treatment completion including, but not limited to other anti-cancer therapies (including radiotherapy) and other immunotherapies (both number and type of medications and treatment indication)
- Laboratory assessments 30 days prior to Blincyto initiation, during Blincyto treatment and up to 30 days after treatment completion (see details in [Appendix B](#)):
  - Biochemistry (including hepatic and renal function assessments)
  - Blood count (including Haemoglobin, Platelets, WBC, Neutrophils, Blasts)
  - Other labs (IgG, coagulation)
- Co-morbid conditions 1 year prior to Blincyto initiation and after Blincyto initiation including but not limited to active or history of central nervous system (CNS) pathology, hepatic impairment, renal impairment, active uncontrolled infections, human immunodeficiency virus (HIV) positivity, hepatitis B and C (both number of comorbidities and type of disease/condition)
- Date of Blincyto treatment initiation
- Graft-versus-host disease and associated prophylaxis for allogeneic HSCT after Blincyto treatment completion

#### **9.4 Data Sources**

All data for this study will be abstracted from patient medical records by site staff using chart reviews at the treatment centre where Blincyto was initiated. The data from these chart reviews will be merged to form a longitudinal cohort for analysis. Since these are data that are collected for patient care, information on Blincyto administration and AEs (eg, type of event, dates of onset, and resolution and severity) are expected to be reasonably complete, although some missing data can be expected. Evaluations of efficacy of treatment, concomitant medications, patient history (including comorbid conditions), and other patient information are also important for patient care and are expected to be available in the medical record.

#### **9.5 Study Size**

The actual number of patients that will be included in the study will be dependent on the approval, reimbursement, and uptake of Blincyto in individual participating countries. We aim to collect data on approximately 200 patients in any of the authorised indications treated with Blincyto with a maximum number of approximately 300 patients treated with Blincyto in total to allow for off-label use.

At the request of CHMP during the marketing authorisation of Blincyto, a subset of adult patients with R/R Ph- B-precursor ALL who had a LFR (first remission  $\geq$  12 months) will

be included in the study in order to provide additional data to evaluate the positive benefit-risk in this subgroup. Although the number of patients in this subgroup is difficult to predict because of uptake and physician and patient preferences, it is estimated that approximately 42 patients of a theoretical 130 adult patients with R/R Ph-B-precursor ALL treated with Blincyto will have had a LFR. These estimates are based on the assumptions presented in [Table 1](#). The number of patients in this subgroup will be assessed during the study and, if required, the patient identification period of the overall study could be extended to allow for additional recruitment of this subgroup of patients.

**Table 1. Estimated Number of Adult Patients With R/R B-precursor ALL who had a Late First-relapse and Were Treated With Blincyto**

|  | Adult Patients with R/R ALL |                                    | Adult Patients with R/R ALL who have had a Late First-Relapse |  |
|--|-----------------------------|------------------------------------|---|--|
|  | n                           | Assumed Proportion of Patients (%) | n   |  |
| Eligible patients who are treated with Blincyto and included in this study | ~130                        | 32% a                   | ~42   |  |

a Based on experience of recruitment in this study described in interim analysis report #3, dated 20 July 2020.

This is a descriptive study and the primary objective of the study is to characterise the safety profile of Blincyto by characterising specified AEs. From MT103-211 study the incidence of specified AEs ranged from 0.5 to 52% (with the exception of 'Worsening of hepatic impairment in patients with hepatic impairment' which was < 0.5%). [Table 2](#) indicates the range of probabilities the study would have with a range of sample sizes to detect at least 1 specified event with the lowest anticipated rates. For example, with an anticipated incidence of one event in one hundred patients or one event in 200 patients and a sample size of 200 patients (at the time of analysis) we can detect a single specified event with probability of 87% or a probability of 63% respectively.

**Table 2. Probability to Detect at Least one AE**

| Anticipated AE Incidence
(patient level) | N = 150 | N = 200 | N = 250 | N = 300 | N = 350 |
|---|---------|---------|---------|---------|---------|
| 1/100 (0.01)                                | 78%     | 87%     | 92%     | 95%     | 97%     |
| 1/200 (0.005)                               | 53%     | 63%     | 71%     | 78%     | 83%     |

Model of rare events using the Poisson distribution assuming no background incidence (Machin et al, 1997)

For binary categorical outcomes we can calculate the expected level of precision for proportion estimates in terms of the half-widths of associated 95% confidence intervals (CI) (Table 3). As above, there is a range in precision of the 95% CIs for a range of sample sizes for each anticipated observed proportion. For example, for the subject incidence of a specified event, the half-width of the 95% CI in a sample size of 350 patients will range between 3.1 and 5.2. Also, from this table we see that for a sample size of patient with LFR of 40 patients we would expect the half width of the 95% CI for a proportion estimate to range from between 9.3% to 15.5%. For example, pooled LFR data from MT103-206 and MT103-211 clinical trials resulted in an overall CR/CRh\* of 88.8% (N = 8/9). If we observe a proportion of 80% for CR/CRh\* in this study then the confidence interval for this estimate would be between 67.6% and 92.4%.

**Table 3. Half-widths of the 95% Confidence Intervals for Proportion Estimates**

| Proportion Estimate | Potential Sample Sizes for Proportion Estimates |        |        |         |         |         |
|---------------------|---|--------|--------|---------|---------|---------|
|                     | N = 20  | N = 40 | N = 60 | N = 350 | N = 200 | N = 150 |
| 10% / 90%           | 13.1  | 9.3    | 7.6    | 3.1     | 4.2     | 4.8     |
| 20% / 80%           | 17.5  | 12.4   | 10.1   | 4.2     | 5.5     | 6.4     |
| 40% / 60%           | 21.5  | 15.2   | 12.4   | 5.1     | 6.8     | 7.8     |
| 50%                 | 21.9  | 15.5   | 12.7   | 5.2     | 6.9     | 8.0     |

Two-sided confidence intervals calculated using the normal approximation

## 9.6 Data Management

Each patient will be assigned a unique identification number at the time of the first data abstraction. This unique identification number will be used to link data to subsequent chart reviews. The data will be abstracted by site staff from patient medical records into a web-based electronic data capture (EDC) system, using an electronic abstraction form that will provide an integrated, transparent tool to facilitate and record centre recruitment, case identification, subject selection and study progress at the centre and patient level.

The EDC system will include electronic case report forms (eCRFs) which will be designed to capture the variables and outcomes of interest. The sponsor will provide protocol-specific training on the eCRF to all study site abstractors in advance of the study data collection period to ensure clarity on the questions and the data to be captured. Some fields in the eCRFs will include drop-down lists (eg, gender, dates), others will be radio buttons (eg, check all disease/conditions in the patient's medical history: diabetes, hypertension, stroke). Data from the serial chart review will be merged to form a longitudinal cohort for analysis.

## **9.7 Data Analysis**

### **9.7.1 Planned Analyses**

Annual summaries of the data will be done for inclusion in specified PSURs estimated to commence with the subsequent PSUR occurring at least 12 months after start of data collection to allow adequate time to accrue treated patients after approval and the start of the study.

### **9.7.2 Planned Method of Analysis**

All analyses will be descriptive. Continuous variables will be summarised by mean, median, standard deviation, 25th percentile, 75th percentile, minimum and maximum. Categorical variables will be summarised by number and percentage. For categorical outcomes, 95% confidence intervals will also be presented where appropriate. For time-to-event endpoints, Kaplan-Meier (KM) curves and estimates (median, 1st and 3rd quartile) of the time-to-event endpoint with 95% confidence intervals will be calculated, if estimable. Six, 12- and 24-month survival proportions and 95% confidence intervals will also be estimated. Tables will be presented for the total patient population (ie, those who meet the eligibility criteria and have at least one dose of Blincyto) split by adult and paediatric patients and for disease subgroups with 15 or more patients, as well as for the subset of patients with LFR. Safety and efficacy data will also be tabulated by the patient subgroups described in Section [9.7.2.3.4](#).

The Medical Dictionary for Regulatory Activities (MedDRA) version 24.1 or later will be used to code all adverse events.

#### **9.7.2.1 Missing or Incomplete Data and Lost to Follow-up**

The eCRFs will be designed to minimize missing data and to optimise the integrity of collected data. However, the data will be abstracted from medical charts used for routine care of patients and so information that is not deemed relevant to the care of that

patient might not be captured in the chart. Therefore, patients' records will not be excluded because of missing data.

## **9.7.2.2 Descriptive Analysis**

### **9.7.2.2.1 Description of Study Enrolment**

Study reporting period, patient number by country and site, and patient number overall and by analysis sets will be tabulated.

### **9.7.2.2.2 Description of Patient Characteristics**

The study population will be characterised by patient and clinical characteristics (eg, age, sex, disease status, prior treatments) including the variables listed in Section 9.3.3.

## **9.7.2.3 Analysis of the Primary, Secondary and Exploratory Endpoint(s)**

### **9.7.2.3.1 Primary Endpoint(s)**

*Specified adverse events:*

Subject incidence proportions (and 95% CIs) for each of the specified adverse events will be summarised. For each of the specified events, incidence will be tabulated by system organ class and preferred term, and preferred term only. Incidence tables will also be presented with respect to time on Blincyto at the patient level (incidence rate) and event level (event rate). KM estimates for time to first onset of each specified event will be provided. A summary of days experiencing specified events and days experiencing resolved/recovered specified events will also be presented. Tables will be presented overall, and by seriousness (serious, fatal) and severity (grade  $\geq 3$ , grade  $\geq 4$ , events leading to discontinuation of Blincyto, events leading to interruption of Blincyto) of event. Tables relating to specified AEs will also be summarised by the patient subgroups listed in Section 9.7.2.3.4. Tables will additionally be presented for specified AEs that are considered related to Blincyto treatment.

*Blincyto medication errors:*

When possible, medication errors may be classified as error with ADR, error without harm, intercepted error and potential error. The number and proportion of medication errors will be summarised overall, by medication error classification, by place of occurrence, and by whether the error resulted in an underdose or overdose of Blincyto. AEs related to medication errors will also be summarised.

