## 7. Rationale and Background

### 7.1 Diseases and Therapeutic Area

Acute lymphoblastic leukaemia (ALL) is a rare malignant disease with an overall incidence of 1.1/100,000 per year. ALL has a bimodal distribution with an early peak at 4 to 5 years of age (incidence of 4.5/100,000 per year) followed by a second gradual increase starting at 50 years and increasing in the 80s (incidence of 2/100,000 per year). It represents 80% of acute childhood leukaemia and 20% of acute leukaemia cases in adults (Pui and Evans 2006; Jabbour et al, 2005; Larson, 2005; SEER, 1975-2009 (Accessed July 2012)). In adults with relapsed or refractory (R/R) B-precursor ALL, treatment options are limited and the prognosis unfavourable. Primary refractory ALL is defined by absence of complete remission (CR) after standard induction therapy. A patient has relapsed ALL if they achieved a CR during upfront therapy and has then relapsed during or after completion of therapy. A similar classification is possible for salvage therapy. Refractory relapse is defined by lack of CR after first salvage therapy. Second relapse or later relapses are defined as relapse after achieving a second CR in

first salvage or later salvage therapies. Currently the only curative option for patients with ALL is allogeneic haematopoietic stem cell transplant (HSCT), which is performed once CR is achieved. Therefore, new therapies that can improve the likelihood of CR are important.

Blinicyto belongs to a new class of bispecific antibody constructs called bispecific T-cell engagers (BiTE®). BiTEs® have been designed to direct T-effector memory cells towards target cells. The proximity induced by the BiTE® triggers target cell-specific cytotoxicity, which closely resembles standard cytotoxic T lymphocyte activation. Blincyto is administered as an intravenous infusion with a single cycle of treatment consisting of 4 weeks of continuous infusion followed by 2 weeks without Blincyto treatment. Blincyto is administered at one of two different dosages (depending on the point in time of the patient's treatment). During Cycle 1, Blincyto is administered at a dose of 9 µg/day on Days 1-7 and 28 µg/day on Days 8-28. A treatment course consists of 2 cycles of Blincyto for induction. Patients who have achieved CR/CRh\* after 2 treatment cycles may receive 3 additional cycles for consolidation treatment.

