In a recent review of the toxicity profiles of chemotherapeutic and other targeted therapies used to treat ALL (Hummel et al, 2016), different regimens were found to have quite different safety profiles. A key conclusion of the review was that the benefit-risk profile of these treatments differs depending both on therapeutic modality, as well as patient and disease characteristics. Safety data from Blincyto clinical trials in the adult R/R ALL population indicate the most common treatment emergent adverse events (TEAEs) (those reported in ≥ 20% of patients overall) were pyrexia, headache, fatigue, peripheral oedema, tremor, nausea, hypokalaemia and diarrhoea. The most frequently reported TEAEs of grade ≥ 3 were febrile neutropenia, neutropenia, leukopenia, anaemia, thrombocytopenia and pneumonia. Patients receiving Blincyto may experience a spectrum of neurologic events, such as seizure, encephalopathy, tremor, apraxia, speech disorders (aphasia, dysarthria), and disorientation. The incidence of patients experiencing neurologic events is greatest within the first week of Blincyto treatment.

Since 2012 Amgen has been providing Blincyto in an expanded access (EA) or compassionate use setting for patients with high unmet medical need when they were not able to enter an Amgen Sponsored Clinical trial and according to country specific regulatory requirements.

EA is a regulatory mechanism by which drugs that are not yet approved for marketing in a given country (including any new indication of an existing marketed product) are made available in that country to seriously ill patients until regulatory approval where no other comparable or satisfactory alternative therapy for a disease or condition exists. An EA request is unsolicited and comes from a treating physician, physician delegate (eg, pharmacist), regulatory agency, or professional medical organisation. EA is generally not employed where there are alternative appropriate mechanisms for the supply of unlicensed therapies to patients in a given country, eg, Pre-Registration Sales. EA also does not apply to an extension study or post-study access to drug for subjects who have participated in an Amgen clinical trial.

For the purposes of this study, EA encompasses the following mechanisms for access, which may vary by country, and include but are not limited to:

- Amgen-sponsored EA protocol(s)
- National settings for cohorts of eligible patients per local regulatory requirements

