#### 9.3.1 Exposure Assessment

All patients included in this study will be or will have been exposed to Blincyto at their entry into the study. Exposure will be described in several ways:

- Duration of exposure (in days)
- Total cumulative dose ( $\mu\text{g}$ )
- Number of cycles completed (0-5)

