#### 9.3.2 Outcome Assessment

##### 9.3.2.1 Primary Endpoint/Outcome

- Incidence of specified AEs (overall, and by severity and seriousness) – All AEs occurring during blinatumomab treatment and up to 30 days after completion of treatment of the following selected risks will be collected if available in the medical record. Events will be reported as diagnosed by the investigator:
  - Neurologic adverse events
  - Opportunistic infections
  - **Cytokine release syndrome**
- Time to onset of first specified AEs
- Summary of duration of specified AEs (all events and resolved/recovered events)
- Proportion of Blincyto administrations with medication errors, defined as an unintended failure in the drug treatment process that leads to, or has the potential to lead to, harm to the patient, identified through medical records. Types of medication errors will also be described. Medication errors include:

- incorrect Blincyto dose administered/prepared (eg, drug concentration, device issues, treatment according to SmPC)
- does not include treatment related to dexamethasone

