**9.7.2.3.3 Other Safety Analyses**

Subject incidence of serious adverse events (SAEs) that occur from 31 days after completion of Blincyto treatment until the start of another anti-cancer treatment, HSCT or for up to 1 year, whichever is earliest, will be tabulated overall and by system organ class and preferred term, and preferred term only. Subject incidence for SAEs will also be summarised by time interval (during Blincyto treatment and 3 month intervals after completion of treatment).

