| 10.3 Are descriptive analyses included?  |  |             |  | 9.7.2.2               |
| 10.4 Are stratified analyses included?   |  |             |  | 9.3.3                 |
| 10.5 Does the plan describe methods for analytic control of confounding?               |  |             |  | 9.3.3                 |
| 10.6 Does the plan describe methods for analytic control of outcome misclassification? |             |  |  |                       |
| 10.7 Does the plan describe methods for handling missing data?                         |             |  |  |                       |
| 10.8 Are relevant sensitivity analyses described?                                      |             |  |  |                       |

Comments:

Data will be collected only from patients exposed to Blincyto. No comparative analyses will be done. Outcome measures will be stratified by patient subgroups and time periods.

| Section 11: Data management and quality control  | Yes                          | No                           | N/A               | Section Number |
|---|-------------------------------------|-------------------------------------|--------------------------|-----------------------|
| 11.1 Does the protocol provide information on data storage? (e.g. software and IT environment, database maintenance and anti-fraud protection, archiving) |             |  |  |                       |
| 11.2 Are methods of quality assurance described?  |  |             |  | 9.9                   |
| 11.3 Is there a system in place for independent review of study results?  |             |  |  |                       |

Comments:

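### Minor: the specified-AE rate tables set events counted to 30 days after treatment against time on Blincyto, and for neurologic events average over an early peak, so the rates depend on treatment length

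*Protocol*

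**What the plan says.** For each specified AE (neurologic events, opportunistic infections, cytokine release syndrome), Section 9.7.2.3.1 plans subject incidence proportions with 95% CIs and KM estimates of time to first onset. It adds rate tables: "Incidence tables will also be presented with respect to time on Blincyto at the patient level (incidence rate) and event level (event rate". The specified-AE tables are repeated by subgroup.

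Section 9.3.2.1 sets the events that belong to the endpoint: "All AEs occurring during blinatumomab treatment and up to 30 days after completion of treatment".

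Section 7.1 describes a cycle as "4 weeks of continuous infusion followed by 2 weeks without Blincyto treatment". Patients in CR/CRh* "after 2 treatment cycles may receive 3 additional cycles for consolidation treatment", and Section 9.3.1 records from 0 to 5 completed cycles. On timing, Section 7.1 states: "The incidence of patients experiencing neurologic events is greatest within the first week of Blincyto treatment".

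On splitting by time, the analysis-plan comment in the ENCePP checklist (Appendix A) says: "Outcome measures will be stratified by patient subgroups and time periods". In the AE analysis text, such intervals are named only in Section 9.7.2.3.3, for SAEs, and there the whole of treatment is one interval.

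**The concern.** Two features make the rates depend on how long a patient was treated, apart from any difference in risk.

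- **Window mismatch, all specified AEs.** The endpoint runs through infusion-free intervals and 30 days past completion, while the stated time base is time on drug. The 30-day tail weighs more when treatment is short.
- **Early peak, neurologic events.** If risk is highest in week 1, each further week adds more person-time than events in proportion, and the average rate falls.

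Treatment length is also tied to response, because consolidation cycles are for patients in remission. The tables are repeated by subgroup, and Section 9.9 uses clinical trial and historical data for context. A reader who sets such rates side by side could take a difference in treatment length for a difference in risk. What is at stake is how descriptive tables are read. No test or primary conclusion depends on it.

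**Working it through.** The protocol states no AE rate, so there is no figure of its own to reproduce.

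**Inputs.** From Section 7.1: 28 days of infusion and 14 days off per cycle. From Section 9.3.2.1: 30 days after completion. Assumed: no interruptions, and treatment running from the first to the last infusion day.

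**Step 1, event window against infusion time.** For c cycles, infusion days = 28c and event window = 42(c - 1) + 28 + 30.

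| Cycles | Infusion days | Window days | Window / infusion |
|---|---|---|---|
| 1 | 28 | 58 | 2.07 |
| 2 | 56 | 100 | 1.79 |
| 5 | 140 | 226 | 1.61 |

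If the hazard is constant and the same off drug as on drug, 1 against 5 cycles gives a rate ratio of 2.07/1.61 = 1.28 from length alone. If time on Blincyto means first to last dose (28 and 196 days), the ratio is (58/28)/(226/196) = 1.80.

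**Step 2, weaker off-drug risk.** Let the off-drug hazard be k times the on-drug hazard (k is not in the documents). Off-drug days in the window are 58 - 28 = 30 and 226 - 140 = 86. Inflation over infusion time is 1 + 30k/28 after 1 cycle and 1 + 86k/140 after 5.

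| k | 1 cycle | 5 cycles | Ratio |
|---|---|---|---|
| 0 | 1.00 | 1.00 | 1.00 |
| 0.25 | 1.27 | 1.15 | 1.10 |
| 0.5 | 1.54 | 1.31 | 1.17 |
| 1 | 2.07 | 1.61 | 1.28 |

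**Step 3, early peak alone.** Count events on infusion only, so that the mismatch plays no part. Let week 1 of cycle 1 have r times the later hazard h, the same in all patients. Event rate = h(7r + 28c - 7)/(28c). The range r = 3 to 10 is assumed.

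- r = 3: 42/28 = 1.50h after 1 cycle and 154/140 = 1.10h after 5, ratio 1.36.
- r = 10: 91/28 = 3.25h and 203/140 = 1.45h, ratio 2.24.
- 1 against 2 cycles: 1.20 (r = 3) to 1.53 (r = 10).
- Assumed overlapping groups (60/30/10% against 20/40/40% at 1, 2 and 5 cycles, mean 1.7 and 3.0 cycles): 1.11 to 1.33.
- Peak recurring at half height in each later cycle, 1 against 5 cycles: 1.15 to 1.38.
- Constant hazard, or a peak recurring in full in every cycle: 1.00.

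**Step 4, patient-level rate.** Section 7.1 speaks of patients with events, so first events matter most. Assume weekly hazards of 0.30 in week 1 and 0.02 later, with person-time censored at the first event.

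| Infusion weeks | First-event rate per 100 patient-weeks | Event rate per 100 patient-weeks | Proportion with event | KM at day 7 |
|---|---|---|---|---|
| 4 | 10.0 | 9.0 | 30.2% | 25.9% |
| 8 | 6.2 | 5.5 | 35.6% | 25.9% |
| 20 | 3.9 | 3.4 | 49.3% | 25.9% |

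Both rates fall with length although weekly risk is identical. The KM estimate at day 7 does not move. With a mild peak (0.20, then 0.10) the event rate falls only from 12.5 to 10.5 between 4 and 20 weeks.

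**Step 5, both features together.** Take the window of Step 1, the peak of Step 3, and off-drug hazard equal to the later on-drug hazard. Event rate = h(7r + window - 7)/(28c). For 1 against 5 cycles: r = 3 gives (72/28)/(240/140) = 1.50, and r = 10 gives (121/28)/(289/140) = 2.09.

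**The case against.** The strongest reply is that time bands, the person-time definition and table footnotes belong in the statistical analysis plan, and that the checklist already announces stratification by time periods. Much of this stands. The protocol says time on Blincyto without defining it further, and nothing rules out week or cycle bands. A reader might infer that it commits to one rate over total treatment time and excludes any split. It does not say so. What does not fall away is that the protocol itself fixes an event window and a time base that do not match, and itself describes the risk as early.

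The reply also points to the proportions and KM estimates in the same paragraph. This stands for first events, and it confines the point to the additional rate tables.

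Three further objections limit the size. The Section 7.1 sentence is about patients, so it does not establish the timing of repeat events. No subgroup is defined by number of cycles, and the documents do not say that the planned subgroups differ in treatment length. Section 9.3.2.1 says which events are collected for the endpoint, while Section 9.7.2.3.1 does not restate which enter the rate numerator, so the mismatch holds on the literal reading only. All three stand.

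Finally, no comparative analyses are planned, and a whole-period rate is a valid descriptive average. That is why the point is minor.

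**Conclusion.** The point holds as a minor, inexpensive improvement to the rate tables in Section 9.7.2.3.1. On the literal reading, the event window is 2.07 times infusion time after 1 cycle and 1.61 times after 5. The rates are then inflated, and unequally so, unless off-drug risk is negligible. For neurologic events a single whole-period rate also falls with longer treatment, unless the peak recurs in full in each cycle.

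The ratios beyond the day counts rest on assumed hazards, off-drug risk and cycle mixes. They show direction and a plausible range, and the actual size cannot be derived from the documents. A reader might infer that the primary safety results are biased. The documents do not support that: the incidence proportions and KM time to first onset do not use this denominator. Nothing is claimed about when opportunistic infections, cytokine release syndrome or repeat events occur.

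**What to change.** Keep the planned tables and add three things to Section 9.7.2.3.1.

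1. Use one window for numerator and denominator: either events on infusion over infusion time, or events to 30 days after completion over time at risk to 30 days after completion, infusion-free intervals included.
2. For neurologic events, add rates for week 1 of cycle 1 and for later on-treatment time, with events and person-time from the same band. Do this overall and in large subgroups only, such as the projected 130 adults with R/R Ph- ALL. Report the planned KM estimate at day 7.
3. State that whole-period rates should not be compared between groups, or with trial or historical data, when treatment length differs.

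The cost is a wording change and a few table columns, from event onset and infusion data already collected. The downside is sparse cells. At an assumed 0.10 events per patient-week, week 1 gives 20 events in 200 patients (exact Poisson 95% CI for the weekly rate 0.061 to 0.154), 13 in 130 (0.053 to 0.171) and 4 in 40 (0.027 to 0.256). At 0.05 to 0.20 per week, a 15-patient subgroup gives 0.75 to 3 events. Small subgroups, including the late first-relapse subset of about 42, should not be banded.

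### Kaplan-Meier for time to first specified AE censors patients who die event-free, so 1-KM overstates the probability of onset; the crude incidence proportion beside it is not affected

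*Protocol*

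**What the plan says.** Section 9.3.2.1 lists both the incidence of specified AEs and "Time to onset of first specified AEs" as primary outcomes. The specified AEs are neurologic events, opportunistic infections and cytokine release syndrome. Ascertainment is limited in time: "All AEs occurring during blinatumomab treatment and up to 30 days after completion of treatment of the following selected risks will be collected".

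Section 9.7.2.3.1 reports the occurrence of these events in three ways:
- a crude proportion: "Subject incidence proportions (and 95% CIs) for each of the specified adverse events will be summarised";
- incidence and event rates over time on treatment;
- for timing, "KM estimates for time to first onset of each specified event will be provided".

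No other method is named for time to onset. Section 9.7.2 makes Kaplan-Meier the general method for time-to-event endpoints and continues: "Six, 12- and 24-month survival proportions and 95% confidence intervals will also be estimated".

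Neither section says how a death before first onset is handled. Section 9.2.4 lists death among the reasons a patient's data end. Where death is meant to count as an event, the protocol says so: RFS and DFS in section 9.3.2.2 both run to relapse or death.

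**The concern.** A patient who dies without a neurologic event, infection or cytokine release syndrome can no longer have one, so death is a competing event. When Kaplan-Meier censors that patient, it treats them as having the same future risk as patients still alive and under observation. The complement of the curve then estimates onset in a hypothetical setting without death, which is higher than the share of treated patients who actually have the event.

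Two results for the same event would then stand side by side in the primary safety analysis, a crude proportion and a higher 1-KM value, with nothing to explain the gap. Deaths in the window are plausible: section 7.1 calls the prognosis in adult relapsed or refractory disease unfavourable, and section 9.9 says data from deceased patients will be included.

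There is also a question of time points. If the 6-, 12- and 24-month sentence in section 9.7.2 were applied to AE onset, most of those times would lie beyond the period in which specified AEs are collected.

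**Working it through.** **The plan's own figures.** The protocol states no figure for the Kaplan-Meier analysis. Its study-size figures in section 9.5 reproduce. Table 2 at N = 200: 1 - exp(-200 × 0.01) = 86.5% and 1 - exp(-200 × 0.005) = 63.2% (stated 87% and 63%). Table 3 at N = 200: 1.96 × √(0.10 × 0.90/200) = 4.2 points, 1.96 × √(0.20 × 0.80/200) = 5.5 and 1.96 × √(0.50 × 0.50/200) = 6.9, as stated. None of these depends on Kaplan-Meier; the half-widths serve below as a yardstick.

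**AE window.** Section 7.1 describes "a single cycle of treatment consisting of 4 weeks of continuous infusion followed by 2 weeks without Blincyto treatment", two induction cycles and up to three more. With 30 days added after the last infusion:
- two cycles: 28 + 14 + 28 + 30 = 100 days;
- four cycles: 3 × 42 + 28 + 30 = 184 days;
- five cycles: 4 × 42 + 28 + 30 = 226 days.

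On the nominal schedule nobody is under AE observation at 12 months, and 6 months is reached only with about four cycles.

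**Size of the excess, constant hazards.** Let F be the true probability of onset by the end of the window and D the probability of dying first, event-free. Section 9.5 quotes incidences of 0.5% to 52% for specified AEs from the pivotal study, which sets the range of F. The protocol gives nothing for D, so 2% to 30% is assumed. With constant hazards and one common window:

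- total cumulative hazard H = -ln(1 - F - D);
- AE part A = H × F/(F + D);
- 1-KM with deaths censored = 1 - exp(-A).

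Example, F = 0.52 and D = 0.30: H = -ln(0.18) = 1.715; A = 1.715 × 0.52/0.82 = 1.087; 1-KM = 1 - exp(-1.087) = 66.3%, an excess of 14.3 points.

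Example, F = 0.10 and D = 0.10: H = -ln(0.80) = 0.223; A = 0.223 × 0.10/0.20 = 0.112; 1-KM = 10.6%, an excess of 0.6 points.

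1-KM (%) at the end of the window:

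| True F | D = 2% | 5% | 10% | 20% | 30% |
|---|---|---|---|---|---|
| 0.5% | 0.51 | 0.51 | 0.53 | 0.56 | 0.59 |
| 10% | 10.1 | 10.3 | 10.6 | 11.2 | 12.0 |
| 20% | 20.2 | 20.6 | 21.2 | 22.5 | 24.2 |
| 52% | 52.7 | 53.7 | 55.6 | 60.1 | 66.3 |

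Against the half-widths at N = 200, the excess stays smaller at 10% incidence (at most 2.0 against 4.2) and at 20% (at most 4.2 against 5.5). At 52% it is 3.6 points with D = 10% and 8.1 with D = 20%, so it passes the 6.9 points stated for a 50% proportion somewhere between those two.

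**Front-loaded events.** Section 7.1 says neurologic events are most frequent in the first week. Assume a 100-day window, a constant death hazard and 80% of the AE hazard in days 1 to 7. For D from 5% to 30%, 1-KM is then 10.1% to 10.5% for F = 10%, 20.2% to 21.1% for F = 20%, and 52.5% to 56.1% for F = 52%. The largest excess is 4.1 points. With 50% of the hazard in week 1, the largest is 60.2 - 52 = 8.2 points.

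In this model the Aalen-Johansen estimate with death as a competing event returns F itself.

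**The case against.** The strongest reply is that the protocol nowhere says in words that deaths are censored, and that such rules commonly sit in a statistical analysis plan, which is not at hand. That is true of the wording. But the protocol itself fixes the estimator and defines the event as AE onset only, while adding death explicitly for RFS and DFS. Kaplan-Meier applied to that definition censors event-free deaths. A later plan could handle death properly only by departing from, or adding to, the method named here.

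A reader might infer that the primary safety incidence as a whole is biased upward. The document does not support that. The probability of having a specified AE is reported first by the crude subject incidence proportion, which does not use Kaplan-Meier; the study size and precision figures rest on event detection and proportions too. The study is descriptive, with no hypothesis or threshold that the curves could move.

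A reader might also infer that the plan commits to 12- and 24-month AE proportions. That is only an ambiguity. The sentence in section 9.7.2 speaks of survival, and section 9.7.2.3.2 refers back to it for efficacy while section 9.7.2.3.1 does not for AEs. It does, however, directly follow a general rule for time-to-event endpoints, so a clarifying line is worthwhile.

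The size cannot be fixed from the document. A particular mortality would be an outside assumption, and so would a claim that opportunistic infections come late and suffer more; the protocol gives the timing of neurologic events only.

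Finally, follow-up for AEs ends 30 days after each patient's own treatment completion. Stopping treatment may be related to AE risk, and a competing-risk estimate does not cure that. This stands as a limit of the fix.

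**Conclusion.** The point holds for the time-to-onset primary outcome and for no other measure. As written, section 9.7.2.3.1 censors event-free deaths, so 1-KM exceeds the true probability of onset whenever such deaths occur. The direction is certain on that reading; the size is not.

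For event-free death shares of 2% to 30% and incidences of 0.5% to 52%, the excess is 0.0 to 0.7 points at 2%, 0.0 to 3.6 at 10% and 0.1 to 14.3 at 30%, under constant hazards and a common window. It is at most 4.1 points if 80% of the AE hazard falls in week 1. It matters for common events with many early deaths and is negligible for rare events or few deaths. The death shares and the week-1 share are assumptions, not protocol figures.

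The 12- and 24-month question is a matter of clarification. On the nominal schedule those times lie outside the AE window, but the protocol does not clearly ask for AE estimates there.

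**What to change.** In section 9.7.2.3.1, replace the Kaplan-Meier estimate with the Aalen-Johansen cumulative incidence of first onset for each specified event. Death without the event is the competing event, and patients are censored at the end of their own AE window. Report it at times inside that window, for example the end of cycle 1 and the end of cycle 2; on the nominal schedule a 6-month value would rest on patients with about four cycles or more.

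In section 9.7.2, add one line stating that the 12- and 24-month proportions apply to the survival endpoints (OS, RFS, DFS) only.

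The cost is wording. Death is already abstracted for OS, so no new data are needed. The downsides are one more method to explain, and that censoring at the end of a treatment-dependent window may still be informative. Because windows differ in length between patients, the new estimate need not equal the crude proportion exactly either, and the report should say so.
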